9.4.2 Safety Endpoints

Safety and tolerability will be assessed by clinical review of all relevant parameters including AEs and postvaccination temperature measurements following any vaccination with V114 or Prevenar 13™.

The safety analysis endpoints include:

- Proportion of participants with solicited injection-site AEs (swelling, redness/erythema, tenderness/pain, and hard lump/induration) from Day 1 through Day 14 following any vaccination with V114 or Prevenar 13™
- Proportion of participants with solicited systemic AEs (irritability, drowsiness/somnolence, hives or welts/urticaria, and appetite loss/decreased appetite) from Day 1 through Day 14 following any vaccination with V114 or Prevenar 13™
- Proportions of participants with the broad AE categories consisting of any AE and a vaccine-related AE from Day 1 through Day 14 following any vaccination with V114 or Prevenar 13™
- Proportions of participants with an SAE, a vaccine-related SAE, and discontinuation due to an AE, and death from Day 1 through 6 months following the vaccination with V114 or Prevenar 13™

- Participants body temperature measured Day 1 (day of vaccination) through Day 7 following any vaccination with V114 or Prevenar 13™

9.5 Analysis Populations

9.5.1 Immunogenicity Analysis Populations

The PP population will serve as the primary population for the analysis of immunogenicity data in this study. The PP population consists of all randomized participants without deviations from the protocol that may substantially affect the results of the immunogenicity endpoint(s). Potential deviations that may result in the exclusion of a participant from the PP population for all immunogenicity analyses include:

- Failure to receive infant series vaccination (V114 or Prevenar 13™ Doses 1 and 2) as per randomization schedule
- Receipt of prohibited medication or prohibited vaccine prior to the first study vaccination

Additional potential deviations that may result in the exclusion from the PP population immunogenicity analyses at a particular time point include:

- Failure to receive Dose 3 of V114 or Prevenar 13™ according to the vaccination schedule required at the time point for the analysis
- Failure to receive Vaxelis™ according to the vaccination schedule required at the time point for the analysis
- Failure to receive the scheduled doses of V114 or Prevenar 13™ (at least 28 days between Doses 1 and 2 [5 months of age to 1 day prior to 6 months of age (+14 days)] [for PD2 and Predose 3 analysis], 12 months to 1 day prior to 13 months of age [+14 days] for Dose 3 [for PD3 analyses])
- Receipt of prohibited medication or prohibited vaccine prior to a blood sample collection
- Collection of blood sample at the time point for the analysis outside of the pre-specified window (as described in Section 1.3)

The final determination on protocol deviations, and thereby the composition of the PP population, will be made prior to the final unblinding of the database. Participants will be included in the vaccination group to which they are randomized for the analysis of immunogenicity data using the PP population.

A supportive analysis using the FAS population will also be performed for the primary immunogenicity endpoints and the secondary endpoints for the evaluation of concomitant vaccines. The FAS population consists of all randomized participants who received all study vaccinations required at the time point for the analysis and have serology result. Participants will be included in the vaccination group to which they are randomized for the analysis of immunogenicity data using the FAS population.

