Administration of meningococcal vaccine is permitted; however, administration of a meningococcal vaccine with a CRM₁₉₇ or other diphtheria toxoid carrier protein (details provided in the Investigator Trial File Binder) should be given after the final blood draw of the study (Visit 5). Meningococcal B vaccine must not be given within 14 days before or after receipt of V114 or Prevenar 13TM, or within 30 days before any scheduled blood draw. During influenza season, it is possible that participants 6 months of age and older could receive an inactivated influenza vaccine. Influenza vaccine should be administered at least 7 days prior to or at least 15 days after the administration of V114 or Prevenar 13TM.

If the participant is scheduled to receive any other nonstudy pediatric vaccine (except for rotavirus, meningococcal, and influenza vaccines), the investigator should discuss this with the Sponsor Clinical Director as soon as possible. All nonstudy vaccinations should be recorded on the appropriate eCRF.

Concomitant vaccines should be administered on the same day as V114 or Prevenar 13TM. Other nonstudy pediatric vaccines should be administered according to the local recommended schedule. Participants enrolled at sites in Norway and Denmark will receive a second dose of VARIVAXTM at Visit 5 according to local vaccination requirements. See Appendix 7 (Section 10.7.2) for country-specific information. If given at a study visit, oral

vaccines should be administered prior to the study vaccine and other injectable vaccines. Precautions must be taken to prevent choking during the administration of oral vaccines. Other injectable vaccines should be given after V114 or Prevenar 13™. To avoid any confounding results, concomitant injectable vaccines and other nonstudy pediatric vaccines should not be administered in the same limb as V114 or Prevenar 13™. Recommended injection-site locations for V114 or Prevenar 13™ and concomitant injectable vaccines being provided in the study are listed in [Table 3](#). Injection -site AEs for the licensed, concomitantly administered vaccines will not be collected.

No other investigational compound or device may be administered at any time during this study without prior approval by the Sponsor.

Table 2 Concomitant Vaccine Schedule

Vaccine Tradename ^{a, b} (Generic Name)	Indication	Visit 1 (~3 months of age)	Visit 2 (~5 months of age)	Visit 4 (~12 months of age)

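### Does the per-protocol rule contradict itself by leaving Dose 2 timing out of the primary PD3 analysis while the Vaxelis rule reaches it?

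*Combined protocol and SAP*

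**What the plan says.** Section 9.5.1 defines the per-protocol (PP) population as "all randomized participants without deviations from the protocol that may substantially affect the results of the immunogenicity endpoint(s". It then lists two kinds of deviation.

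- **For all immunogenicity analyses:** "Failure to receive infant series vaccination (V114 or Prevenar 13™ Doses 1 and 2) as per randomization schedule", and prohibited medication or vaccine before the first study dose.
- **By time point**, introduced with "Additional potential deviations that may result in the exclusion from the PP population immunogenicity analyses at a particular time point include". One bullet gives the timing windows for V114 or Prevenar 13. The Dose 2 part reads "5 months of age to 1 day prior to 6 months of age (+14 days)] [for PD2 and Predose 3 analysis", together with a minimum interval of 28 days between Doses 1 and 2. The Dose 3 part reads "12 months to 1 day prior to 13 months of age [+14 days] for Dose 3 [for PD3 analyses". A separate bullet reads "Failure to receive Vaxelis™ according to the vaccination schedule required at the time point for the analysis".

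Section 6.5 links the two vaccines: "Concomitant vaccines should be administered on the same day as V114 or Prevenar 13TM". Table 2 schedules Vaxelis at Visits 1, 2 and 4, the visits at which the pneumococcal vaccine is given.

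H1 to H5 are all tested at PD3. PD2 and Predose 3 carry no hypothesis. Section 9.5.1 also provides a supportive full analysis set (FAS) for the primary and Vaxelis endpoints. It requires the doses due by that time point and a serology result, with no timing window.

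**The concern.** Read literally, the time-point tags mean that the Dose 2 window governs no hypothesis test. An infant whose second dose fell well outside the window leaves the PD2 and Predose 3 analyses, but has no pneumococcal timing ground for leaving the PD3 analysis. The same infant will normally have received Vaxelis late on the same day, and the Vaxelis bullet is not limited to the earlier time points. If its reference to the schedule includes timing, that infant has a ground for exclusion at PD3 through Vaxelis but none through the vaccine under test.

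At stake would be the membership of the primary population in a trial of a schedule at about 3, 5 and 12 months. In a non-inferiority comparison, keeping infants who departed from the schedule can pull the arms together. Late visits were also a real prospect: the amendment summary says that the pandemic kept many participants from attending within their windows.

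**Working it through.** **1. Can an infant be both in and out?** The bullets are alternative grounds for exclusion. An infant who escapes the pneumococcal timing bullet at PD3 is not thereby admitted, and any other ground can still remove the infant. If the Vaxelis ground applies, the infant is out. If it does not, the general definition decides. Neither route gives two answers at once.

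**2. Is there a consistent reading?** The Vaxelis bullet and the bullet on failure to receive Dose 3 refer to the schedule in the same words. A further bullet then gives the Dose 3 age window. If the shared phrase already covered timing, that window would be redundant. The FAS definition uses similar language for receipt alone. So the Vaxelis bullet can mean that the required doses were received. It states no day window. On that reading, pneumococcal timing is set time point by time point and Vaxelis is a receipt rule, with no conflict.

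**3. Do the tags make sense?** Section 4.2.1.1 gives PD2 as the response to the primary series, Predose 3 as persistence, and PD3 as the anamnestic response. Dose 2 timing for the first two and Dose 3 timing for the third fits that scheme.

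**4. Does the 28-day interval matter?** Dose 1 is given by day 111. Five months of age is 150 to 153 days. The shortest on-schedule gap is 150 − 111 = 39 days, so only the age window has any effect for infants vaccinated on schedule.

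**5. Do the plan's figures reproduce?** Inputs are from Section 9.9.1 and Table 8: 590 per arm, evaluability 80% at PD2 and 75% at PD3, one-sided alpha 0.025.

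- Evaluable: 590 × 0.80 = 472; 590 × 0.75 = 442.5, stated as 443.
- H5 power per antigen, by the Farrington-Manning method with common response rate p and absolute margin m: Φ[(m − 1.96·s0)/s1]. Here s1 = √[2p(1 − p)/n], and s0 uses the two rates fitted under the null.
- For p = 0.97, m = 0.05, n = 443, the null rates are 0.9312 and 0.9812. Then s0 = √[(0.9312 × 0.0688 + 0.9812 × 0.0188)/443] = 0.01365 and s1 = √(0.0582/443) = 0.01146. Power is Φ[(0.05 − 0.02675)/0.01146] = Φ(2.03) = 0.9787.
- The other cells are 0.999995 (95%, margin 10%) and 0.99797 (90%, margin 10%).
- Joint power over the 11 antigens, taken as independent: 0.999995² × 0.9787⁴ × 0.99797⁵ = 0.908, against 90.9% stated. An unpooled variance gives 96.1% and does not reproduce it.
- H1 over 13 serotypes (95% in both arms, margin 0.1): 0.999995¹³ = 0.9999. H3 (SD 1.1 on the log scale, true ratio 1.0, margin 0.5) exceeds 0.9999. Both agree with the stated figure of over 95%.

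**6. What would extending the Dose 2 window to PD3 cost?** The documents give no share of infants with an off-window Dose 2, so the share x below is an assumption, taken on top of the 75% evaluability. The remaining number is n = 443 × (1 − x).

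| x | n per arm | H1, 13 serotypes | H5, 11 antigens |
|---|---|---|---|
| 0 | 443 | 99.99% | 90.8% |
| 2% | 434 | 99.99% | 89.8% |
| 5% | 421 | 99.99% | 88.1% |
| 10% | 399 | 99.97% | 84.6% |
| 20% | 354 | 99.87% | 74.9% |

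H3 stays above 99.8% throughout. If the 75% already allows for such exclusions, the loss is smaller or nil.

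**The case for a change.** The best case for a change is that the primary population should be fixed by rule. The all-analyses bullet on Doses 1 and 2 most naturally concerns receiving the allocated vaccine, since a separate timing bullet would otherwise be needless. The FAS has no timing window either, so under the literal tags neither analysis set removes an infant from the primary comparison for a late pneumococcal Dose 2. The Vaxelis bullet does not say whether it covers timing, or whether it applies to pneumococcal endpoints, Vaxelis endpoints or both. The permissive wording leaves the matter to judgement.

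Much of that stands as a description of the text. It does not establish harm. Sections 9.2 and 9.5.1 have deviations identified and PP membership settled before final unblinding, so the judgement cannot follow the results by arm. The general definition lets the team drop a late Dose 2 that could substantially affect the PD3 result.

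The dilution argument is a general tendency with nothing in the documents to size it. Under the extreme assumption that the arms do not differ at all among 5% of infants, a true deficit of 10 points would appear as 0.95 × 10 = 9.5 points. Infants in the PD3 analysis who differ only in Dose 2 timing have still had all three doses, with Dose 3 and the blood draw on schedule, so a complete loss of the difference is hard to credit.

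**Conclusion.** The concern does not hold as a contradiction. Section 9.5.1 leaves unstated whether an off-window Dose 2 affects PD3 membership and whether the Vaxelis bullet concerns timing or receipt. This is missing detail that the study team can settle sensibly, and blind, when it fixes the PP list. A coherent reading is available, and the documents do not show whether the narrower tag was deliberate, so they do not show an error.

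No sample size or power figure is affected. Writing Dose 2 timing into the PD3 rule would be a debatable trade-off: infants leave the primary set, and H5 power falls by about 1.0 point at an assumed 2% removed (90.8% − 89.8%), 2.7 at 5% (90.8% − 88.1%) and 6.2 at 10% (90.8% − 84.6%), against a gain that has not been demonstrated. These losses assume independence across antigens, the Table 8 response rates, and removals beyond the 25% already allowed for. Power for H1 and H3 is insensitive to the choice.

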9.5.2 Safety Analysis Populations

Safety analyses will be conducted in the APaT population, which consists of all randomized participants who received at least one dose of study vaccination. Participants will be included in the group corresponding to the study vaccination they actually received for the analysis of safety data using the APaT population. This will be the group to which they are randomized except for participants who take incorrect study vaccination; such participants will be included in the vaccination group corresponding to the study vaccination actually received. Safety parameters for cross-treated participants (ie, those who received vaccinations of both V114 and Prevenar 13TM) will be summarized separately.

At least 1 temperature measurement obtained after study intervention is required for inclusion in the analysis of temperature.

9.6 Statistical Methods

Statistical testing and inference for immunogenicity and safety analyses are described in Section 9.6.1 and Section 9.6.2, respectively. Unless otherwise stated, all statistical tests will be conducted at the $\alpha=0.05$ (2-sided) level. Section 9.6.3 describes how demographic and baseline characteristics will be summarized.

9.6.1 Statistical Methods for Immunogenicity

This section describes the statistical methods that address the primary, secondary, and exploratory immunogenicity objectives.

Primary Endpoint

Primary Endpoints/Hypotheses (H1 and H2)

The primary endpoint, anti-PnPs serotype-specific IgG responses at or above the threshold value of 0.35 μ g/mL for 13 shared serotypes contained in V114 and Prevenar 13TM at 30 days PD3 will be assessed via the following non-inferiority hypotheses:

$$H_0: p_1 - p_2 \leq -0.1 \text{ versus}$$

$$H_1: p_1 - p_2 > -0.1,$$

and for the 2 unique serotypes contained in V114, the primary endpoint, anti--PnPs IgG responses will be assessed via the following superiority hypotheses:

$$H_0: p_1 - p_2 \leq 0.1 \text{ versus}$$

$$H_1: p_1 - p_2 > 0.1,$$

where p_1 is the response rate for the V114 group and p_2 is the response rate for the Prevenar 13TM group. V114 is non-inferior to Prevenar 13TM if the lower bound of the 2-sided 95% CI for the between-treatment differences (V114 minus Prevenar 13TM) is greater than -0.1 for the 13 shared serotypes, and superior to Prevenar 13TM if the lower bound of the

2-sided 95% CI for the between-treatment differences (V114 minus Prevenar 13TM) is greater than 0.1 for the 2 unique serotypes contained in V114. The Miettinen and Nurminen (M&N) method (1985), an unconditional, asymptotic method, will be used for this analysis [Miettinen, O. and Nurminen, M. 1985].

Primary Endpoints/Hypotheses (H3 and H4)

The primary endpoint, anti-PnPs serotype-specific IgG GMCs for 13 shared serotypes contained in V114 and Prevenar 13TM at 30 days PD3 will be assessed via the following non-inferiority hypotheses:

$$H_0: GMC_1/GMC_2 \leq 0.5 \text{ versus}$$
$$H_1: GMC_1/GMC_2 > 0.5,$$

and for the 2 unique serotypes contained in V114, the primary endpoint, anti--PnPs IgG GMCs will be assessed via the following superiority hypotheses:

$$H_0: GMC_1/GMC_2 \leq 2.0 \text{ versus}$$
$$H_1: GMC_1/GMC_2 > 2.0$$

where GMC_1 is the anti-PnPs serotype-specific IgG GMCs for V114 group and GMC_2 is the anti-PnPs serotype-specific IgG GMCs for the Prevenar 13TM. For the 13 shared serotypes, V114 is non-inferior to Prevenar 13TM if the lower bound of the 2-sided 95% CI for the GMC ratios (V114/Prevenar 13TM) is greater than 0.5; for the 2 unique serotypes, V114 is superior to Prevenar 13TM if the lower bound of the 2-sided 95% CI for the GMC ratios (V114/Prevenar 13TM) is greater than 2.0. Estimation of the IgG GMC ratios and computation of the corresponding 95% CIs will be calculated using t--distribution with the variance estimate from a linear model utilizing the log-transformed antibody concentrations as the response and a single term for vaccination group.

Secondary Endpoints

Secondary Endpoint/Hypothesis (H5)

For this hypothesis (H5), the antigen-specific response rates for participants administered V114 concomitantly with VaxelisTM will be compared with participants administered Prevenar 13TM concomitantly with VaxelisTM at 30 days PD3 via the following non-inferiority hypotheses:

$$H_0: p_1 - p_2 \leq \delta \text{ versus}$$
$$H_1: p_1 - p_2 > \delta$$

where p_1 is the response rate for the V114 group, p_2 is the response rate for the Prevenar 13TM group, and δ is the prespecified non-inferiority margin and the values of δ are listed in [Table 8](#). VaxelisTM administered concomitantly with V114 is non-inferior to VaxelisTM administered concomitantly with Prevenar 13TM if the lower bound of the 2-sided 95% CI for the between-treatment difference between V114 vs Prevenar 13TM greater than δ .

The M&N method (1985) will be used for this analysis.

Other Secondary Endpoints/Exploratory Endpoints

Other secondary/exploratory objectives include the evaluation of anti-PnPs serotype-specific IgG GMCs at 30 days PD2 and Predose 3, anti-PnPs serotype-specific IgG response rates at 30 days PD2, and anti-PnPs serotype-specific OPA GMTs and response rates at 30 days PD2, Predose 3, and 30 days PD3. The evaluations of these objectives will be performed within each vaccination group separately. Descriptive statistics with point estimates and within-group 95% CIs will be provided. For the continuous endpoints, the point estimates will be calculated by exponentiating the estimates of the mean of the natural log values and the within-group CIs will be derived by exponentiating the bounds of CIs of the mean of the natural log values based on the 1-sample t-distribution. For the dichotomous endpoints, the within-group CIs will be calculated based on the exact method proposed by Clopper and Pearson [CLOPPER, C. J. and PEARSON, E. S. 1934].

Reverse Cumulative Distribution Curves for IgG concentrations at 30 days PD3 will be graphically displayed by serotype.

A detailed analysis strategy for immunogenicity endpoints is listed in [Table 6](#).

Table 6 Analysis Strategy for Immunogenicity Variables

Endpoint/Variable (Description, Time Point)	Primary vs. Supportive Approach [†]	Statistical Method	Analysis Population	Missing Data Approach
Primary Endpoint (H1 – H2)				
Anti-PnPs serotype-specific IgG response rates at 30 days PD3	P	Miettinen and Nurminen (estimate, 95% CI, p-value)	PP	Missing data will not be imputed
	S		FAS	
Primary Endpoint (H3 – H4)				
Anti-PnPs serotype-specific IgG GMCs at 30 days PD3	P	t-distribution with the variance estimate from a linear model [‡] (estimate, 95% CI, p-value)	PP	Missing data will not be imputed
	S		FAS	
Secondary Endpoint (H5)				
Antigen-specific response rates for all antigens included in Vaxelis TM at 30 days PD3 of V114 or Prevenar 13 TM	P	Miettinen and Nurminen (estimate, 95% CI, p-value)	PP	Missing data will not be imputed
	S		FAS	
	S		FAS	

Endpoint/Variable (Description, Time Point)	Primary vs. Supportive Approach [†]	Statistical Method	Analysis Population	Missing Data Approach
Other Secondary Endpoints				
Anti-PnPs serotype-specific IgG response rates and GMCs for the 15 serotypes contained in V114 at 30 days PD2	P	Descriptive Statistics (estimate, 95% CI)	PP	Missing data will not be imputed
Anti-PnPs serotype-specific OPA GMTs and response rates at 30 days PD3	P	Descriptive Statistics (estimate, 95% CI)	PP	Missing data will not be imputed
CI = confidence interval; FAS = Full Analysis Set; GMC = geometric mean concentration; GMT = geometric mean titer; H = hypothesis; IgG = Immunoglobulin G; OPA = opsonophagocytic activity; PD = postdose; PnPs = pneumococcal polysaccharide; PP = Per-Protocol.				

† P = Primary approach; S = Supportive approach.
 
‡ Estimation of the IgG GMC ratios and computation of the corresponding 95% CIs will be calculated using t-distribution with the variance estimate from a linear model utilizing the log-transformed antibody titers as the response and a single term for vaccination group.
				

